The starting dose and schedule in the feasibility part for combination treatment with futibatinib and pembrolizumab will be the RPTD of futibatinib monotherapy (i.e., 20mg once daily (QD)) and the approved dose of pembrolizumab (i.e., 200mg every 3 weeks (Q3W), respectively (Table 1). If considered intolerable during cycle 1 (21 days), a lower dose of futibatinib in combination with pembrolizumab 200mg Q3W will be explored as shown in Table 1. Dose modifications of futibatinib are not permitted during cycle 1 in the feasibility part.

Table 1: Dose Level for futibatinib and pembrolizumab for the feasibility part

Dose level	Pembrolizumab	Futibatinib
Level 1 (starting dose)	200 mg Q3W	20 mg QD
Level -1	200 mg Q3W	16 mg QD
Level -2	200 mg Q3W	12 mg QD

Based on the results observed in the feasibility part, the dose of futibatinib in combination with pembrolizumab 200mg Q3W will be determined for the expansion part.

Current Status

As of 23 January 2021, a total of 13 patients were enrolled and treated in Study 10059030. This included 11 patients enrolled in the feasibility part and 2 patients enrolled in the expansion part. All patients enrolled were treated with futibatinib 20mg QD in combination with pembrolizumab 200mg Q3W.

Safety

All 13 patients included in the analysis experienced at least 1 treatment-emergent adverse event (TEAE). No Dose limiting toxicity were observed in any of these patients. Table 2 summarizes the most common AEs ($\geq 20\%$ incidence rate) observed as of the cut-off date in this study regardless of relationship to study treatment.

The most frequently reported TEAE was hyperphosphatemia, with an incidence of 92.3% (including 4 patients [30.8%] with Grade ≥ 3 AEs defined as serum phosphate level $>7\text{mg/dl}$ irrespective of clinical symptoms). Hyperphosphatemia is a known on-target effect of FGFR inhibitors and has been reported to a similar frequency and grade for single agent treatment with futibatinib.

Other common AEs ($\geq 20\%$ incidence rate) included constipation, diarrhea, nausea, stomatitis, decreased appetite and dermatitis acneiform.

Table 2: Adverse Events by Preferred Term All-Grade Incidence $\geq 20\%$ Regardless of Relationship to Study Treatment (Safety Population)

MedDRA(ver.23.1) System Organ Class Preferred Term	TAS-120+Pembro (N=13)	
	All Grades	>/=Grade 3
	N (%)	N (%)
Any Event	13 (100.0)	7 (53.8)
Gastrointestinal disorders	13 (100.0)	1 (7.7)
Constipation	3 (23.1)	0 (0.0)

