5.6 Evaluation of Toxicity

This is an open-label phase II study. MD Anderson will have access to the Safety Data on a regular basis.

The lead-in patients have to be evaluated for DLT. The DLT window is 21 days.

Hematological DLT is defined as study drug-related toxicity:

- Platelets < 25,000 / μ L or bleeding associated with platelets < 50,000 / μ L
- Grade 4 neutropenia lasting 7 or more days
- Neutropenic fever

Non-hematological toxicities are graded using NCI CTCAE v5.0 toxicity criteria and the DLT is defined as study drug-related toxicity:

- Grade 3 or greater non-hematological toxicity other than nausea, vomiting, or fatigue
- Grade 3 or greater clinically significant electrolyte abnormalities
- Grade 3 nausea and vomiting related to study drug treatment that is not controlled at 72 hours despite appropriate antiemetic therapy
- Evaluation of liver toxicity as defined by Hy's Law:
 - The drug causes hepatocellular injury with ALT or AST \geq 3 x ULN or baseline
 - Total Bilirubin $>$ 2 x ULN, without initial findings of cholestasis (elevated serum alkaline phosphatase < 2 x ULN)
 - No other reason can be found to explain the combination of increased ALT/AST and total bilirubin, such as viral hepatitis, alcohol abuse, ischemia, preexisting liver disease, or another non-study agent capable of causing the observed injury
- Persistent Grade 2 toxicity or laboratory tests such as hyperphosphatemia or hypophosphatemia that cannot be resolved by administering phosphate binders, and requires a dose reduction will be considered a DLT if the treating physician and the principal investigator concur.
- Any death not clearly due to underlying disease or extraneous causes

The following types of toxic effects would not be considered in the definition of DLT:

- Alopecia, or nausea and vomiting in the absence of appropriate antiemetics, or insomnia, obesity/weight gain, infertility, amenorrhea, galactorrhea, or glucose intolerance that is believed to be due to dexamethasone used as antiemetic.
- The laboratory tests if asymptomatic despite being Grade 3, except for phosphate levels as described above.

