- **Possible** - the adverse event may be related to the investigational agent(s).
- **Unlikely** - The adverse event is doubtfully related to the investigational agent(s).
- **Unrelated** - The adverse event is clearly NOT related to the investigational agent(s).

Outcome and sequelae, and action taken, including but not limited to changes in the dosing regimen of the assigned treatment medication. Details of changes to the dosage schedule or any corrective treatment should be recorded.

If an adverse experience increases in frequency or severity during a study period, a new record of the experience will be started, if felt to be related to study drug. Abnormal laboratory results and/or vital signs will not be recorded as adverse experiences unless deemed clinically significant by the Investigator. The CTEP active version of NCI Toxicity Criteria may be used by the Investigator as a guide in determining the severity of abnormal laboratory values.

Assessment of Intensity: Maximum intensity should be assigned to an adverse experience. Intensity will be assigned a grade of 1-5 based upon the most current version of the NCI Common Terminology Criteria (<http://www.ctep.info.nih.gov>). Final arbitration of intensity in cases of differing assessments by different practitioners will be the attending physician and/or the principal investigator. Day to day fluctuations of intensity may not be recorded but rather the worst grade over the longest time period may be recorded.

- **Grade 1:** Mild: discomfort present with no disruption of daily activity, no treatment required beyond prophylaxis.
- **Grade 2:** Moderate: discomfort present with some disruption of daily activity, require treatment.
- **Grade 3:** Severe: discomfort that interrupts normal daily activity, not responding to first line treatment.
- **Grade 4:** Life Threatening: discomfort that represents immediate risk of death
- **Grade 5: Death**

Assessment of Causality: Every effort should be made to explain each adverse experience and to assess its relationship, if any, to the study medication. Assignment of causality will be made using the following question whether there is a reasonable possibility that the event may have been caused by the study medication.

This is a Phase II study, AEs will be recorded as per the guidelines for phase II on the [Table 10](#) below:

Table 10: Recommended Adverse Event Recording Guidelines

Attribution	Grade 1	Grade 2	Grade 3	Grade 4	Grade 5

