6 REGULATORY AND REPORTING REQUIREMENTS

6.1 Evaluation of Toxicity/Adverse Events

Evaluation of toxicity will be done in accordance with the National Cancer Institute's Common Terminology Criteria for Adverse Events (CTCAE) version 5.0 (https://ctep.cancer.gov/protocolDevelopment/electronic_applications/ctc.htm#ctc_50).

All clinically insignificant abnormal laboratory tests will not be documented. Grade 1 toxicities (related or unrelated) will not be collected or documented as these are not considered clinically significant in this patient population and/or they are expected for these study agents. Grade 2 or higher toxicities that are felt to be treatment related and unexpected will be documented. Unless otherwise documented in the electronic medical record as clinically significant and study drug related, all laboratory abnormalities will be assumed to be related to the patient's other co-morbid conditions, prior therapies, other concomitant therapies/medications, or underlying cancer.

The principal investigator is responsible for monitoring the safety of patients who enroll in the study. All AEs occurring after any administration of the study drug will be followed until resolution, stabilization, death, loss to follow up, or commencement of new therapy. The descriptions and grading scales found in the revised NCI CTCAE version 5.0 will be used for adverse event reporting. A copy of the CTCAE version 5.0 can be downloaded from the CTEP web site (<http://ctep.cancer.gov/reporting/ctc.html>).

The investigator (or physician designee) is responsible for verifying and providing source documentation for all adverse events and assigning the attribution for all adverse events for subjects enrolled. Attribution and outcome should be assigned separately for each drug and noted on the CRF.

The Investigator is responsible for completing a toxicity/efficacy summary report, and submitting it to the IND Office Medical Affairs and Safety Group, for review and approval.

Planned interim analyses occur at two time points: one cohort for the lead-in patients after all patients have completed the initial 21 days of study treatment (lead-in cohort summary), and the other for patients who are enrolled to the stage I (stage I cohort summary). The cohort summary should be submitted before study advancing/changing dose levels. A copy of the cohort summary should be placed in the Investigator's Regulatory Binder under "sponsor correspondence".

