Causal Relationship with Study Drug

The causal relationship between an AE and study drug will be assessed using the following 2-point scale, taking into account the patient's condition, medical history, concomitant medications, and the temporal relationship between study drug administration and onset of the event, **as well as biological plausibility**.

An AE is considered to be “Related” if the event follows a reasonable temporal sequence from administration of study drug and there is a reasonable possibility that at least one of the following conditions is true:

- A positive dechallenge: This means that the event improves or resolves after the drug is stopped (temporarily or permanently).
- A positive rechallenge: This means that the event reappears after the drug is restarted.
- The event cannot be reasonably explained by the patient’s clinical state and/or other therapies administered.
- A single occurrence of an event that is uncommon and known to be strongly associated with drug exposure (e.g., angioedema, Stevens-Johnson syndrome).

An AE is considered to be “Not related” if there is no reasonable possibility that at least one of the following conditions is true:

- The event occurred prior to study drug administration.
- There is no reasonable possibility that the study drug caused the event. (“no reasonable possibility” means there is no evidence to suggest a causal relationship between the study drug and the AE)
- The event does not follow a reasonable temporal sequence from administration of study drug and could have been produced by a documented pre-existing condition, concomitant medication or patient’s clinical state.

Outcome of Adverse Events

Record the outcome of AEs as follows:

• Resolved	• Not resolved	• Fatal
• Recovered with sequelae	• Recovering	• Unknown

Follow-up of Adverse Events

Any ongoing AEs should be followed until the earliest occurrence of one of the following:

- The AE has resolved or stabilized
- Completion of safety follow-up visit
- Start of new antitumor therapy
- Withdrawal of consent
- Death
- Other (e.g., transfer to another hospital)

Laboratory Assessments

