6.5 Investigator Reporting Responsibilities

The conduct of the study will comply with all FDA safety reporting requirements.

IND Annual Reports (DSUR)

If the FDA has granted an IND number, it is a requirement of 21 CFR 312.33, that an annual report is provided to the FDA within 60-days of the IND anniversary date. 21 CFR 312.33 provides the data elements that are to be submitted in the report.

TAIHO and/or partner shall be responsible for the preparation, content and submission of a Development Safety Update Report (DSUR). TAIHO may delegate the preparation of the DSUR to a third party. If requested, TAIHO shall provide the Investigator with the final version of this report within 15 calendar days after submission to health agencies and ethics committees.

All adverse experience reports must include the patient number, age, sex, weight, severity of reaction (mild, moderate, severe), relationship to drug (probably related, unknown relationship, definitely not related), date and time of administration of test medications and all concomitant medications, and medical treatment provided. The investigator is responsible for evaluating all adverse events to determine whether criteria for "serious" and as defined above are present.

The Annual Report should be filed in the study's Regulatory Binder.

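### The Not related definition in Section 6.1 is inverted, laboratory abnormalities default to other causes, and no stated cut-point links the three causality lists to DLT counting

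*Combined protocol and SAP*

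**What the plan says.** Causality is described in several places in the combined protocol and SAP.

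- **Section 6.1, Causal Relationship with Study Drug.** "The causal relationship between an AE and study drug will be assessed using the following 2-point scale". An event is Related if the timing is reasonable and at least one supporting condition may hold, such as a positive dechallenge or rechallenge. An event is Not related "if there is no reasonable possibility that at least one of the following conditions is true". Three conditions follow. The first is "The event occurred prior to study drug administration"; the second is that the drug could not reasonably have caused the event; the third is that the timing does not fit and another cause could explain it.
- **Section 6.1, opening text.** Unless the medical record documents clinical significance and drug relationship, "all laboratory abnormalities will be assumed to be related to the" patient's comorbidities, other therapies or cancer.
- **Section 5.6.** Attribution has five levels: Definite, Probable, Possible, Unlikely and Unrelated. Table 10 uses them to decide which events are recorded.
- **Section 6.5.** Adverse experience reports carry a three-category field: "relationship to drug (probably related, unknown relationship, definitely not related".
- **Section 5.6, DLT definition.** "Hematological DLT is defined as study drug-related toxicity", and the non-hematological definition carries the same requirement. Neither names a scale or a cut-point.
- **Section 2.4.** "Hyperphosphatemia is a known on-target effect of" FGFR inhibitors.

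Section 1.2 makes adverse events, expressly including laboratory tests, a primary endpoint.

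**The concern.** Attribution does two jobs here. It decides which toxicities appear as treatment-related in a primary endpoint, and it feeds the DLT counts behind the lead-in rule (continue with at most 1 DLT in 6) and the rule that ends a dose level when more than 30% of patients have DLTs (Sections 4.1, 7.1 and 7.3).

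A definition that places the same event in both categories, or in neither, cannot be applied consistently. A standing presumption against the drug for laboratory findings is harder to defend when the best-known toxicity of the class is a laboratory finding. And if two assessors use different lists, nothing says how a score of Unlikely, or an unknown relationship, should be counted toward a DLT.

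**Working it through.** **Step 1. The two limbs of Section 6.1.** Let A = began before dosing, B = no reasonable possibility that the drug caused it, C = timing does not fit and another cause could explain it. As written, Not related = NOT (A or B or C). The evident intention is Not related = (A or B or C). Related = reasonable timing AND a reasonable possibility of at least one supporting condition.

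| Event | Related | Not related, as written | Not related, as intended |
|---|---|---|---|
| Well timed, drug-caused (A, B, C all false) | Yes | Yes | No |
| Began before dosing (A true) | No | No | Yes |
| Well timed, but drug cause excluded (B true) | No | No | Yes |
| Timing does not fit, other cause (B and C true) | No | No | Yes |

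The drug-caused event falls in both classes. Each event that ought to be Not related falls in neither.

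**Step 2. The laboratory presumption against the protocol's own data.** Section 2.4, Table 2, reports hyperphosphatemia in 12 of 13 patients on this combination: 12/13 = 92.3%, with 4/13 = 30.8% at Grade 3 or above. Both printed figures reproduce. Under the Section 6.1 presumption, silence in the chart assigns such a finding to another cause.

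In Table 10, phase II recording of Unrelated and Unlikely events starts at Grade 3; Grade 1 and 2 events are recorded from Possible upward. A Grade 1 or 2 laboratory event presumed unrelated can therefore go unrecorded, and later review could not fully recover it. Section 6.1 separately says that Grade 1 events are not collected at all, so the practical loss is mainly at Grade 2.

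**Step 3. The three lists.** Section 5.6 has five categories, Section 6.1 two and Section 6.5 three. No table or sentence maps one to another. The unknown-relationship category in Section 6.5 has no counterpart in the other two.

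**Step 4. What mislabelling could do to the lead-in rule.** The plan gives no figure for this, so both inputs are assumptions: the true DLT rate p, and the share m = 25% of DLTs labelled unrelated. With effective rate q = p(1 − m),

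P(at most 1 DLT in 6) = (1 − q)^6 + 6q(1 − q)^5.

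Example at p = 10%: with full attribution, 0.9^6 + 6(0.1)(0.9^5) = 0.531 + 0.354 = 0.886. With q = 0.075, 0.925^6 + 6(0.075)(0.925^5) = 0.626 + 0.305 = 0.931.

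| Assumed true DLT rate | Full attribution | 25% labelled unrelated |
|---|---|---|
| 10% | 88.6% | 93.1% |
| 20% | 65.5% | 77.6% |
| 30% | 42.0% | 59.4% |
| 40% | 23.3% | 42.0% |

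The efficacy design is untouched: its 4.87% type I error and 86.20% power (Table 11) reproduce exactly and do not depend on attribution.

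**The case against.** A reader might infer that these passages make the DLT count wrong in one direction, so that the regimen must look safer than it is. The documents do not support that, for these reasons.

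- The Related limb is worded correctly, so a drug-caused event still qualifies as Related. The inversion produces contradiction, not a demonstrated undercount, and its intended meaning is easy to guess.
- Section 5.6, where DLTs are defined, has its own sound question: could the study medication reasonably have caused the event? Nothing ties DLTs to the faulty limb in Section 6.1.
- A working split at Possible already exists. Section 5.6 uses it for laboratory findings, Table 10 for recording, and Section 6.2 for 24-hour reporting. The list in Section 6.5 concerns report content, not DLT decisions.
- The laboratory presumption can be overridden by documentation. Section 6.1 also makes the investigator responsible for attributing every adverse event, requires review of all laboratory results, and treats an abnormality needing intervention as an adverse event. Table 4 links raised phosphate to phosphate-lowering therapy, and Section 5.6 has a specific phosphate DLT item that needs physician and principal investigator agreement.
- Not every DLT item turns on attribution in the same way: the death item counts any death not clearly due to other causes.
- The 92.3% is an all-grade incidence in another study and says nothing about misattributed DLTs. Section 2.4 reports no DLTs in those 13 patients, and none in the urothelial study, where 3 of 4 patients had completed cycle 1.

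All of this stands, and it limits the consequence. It does not repair the negation, remove the presumption where the chart is silent, or state which categories count as drug-related for a DLT.

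**Conclusion.** The point holds as a contradiction between stated rules, with one element that has a direction. The Not related definition cannot be applied as written. The laboratory presumption can lead to under-attribution, and in part to non-recording, of treatment-related laboratory toxicity in a primary endpoint. The three lists are unmapped, and the split at Possible used elsewhere is never applied to DLTs.

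Its size cannot be estimated from the documents. On the assumption that 25% of DLTs are labelled unrelated, the chance of passing the lead-in rises by 4.5 points at a true rate of 10%, 12.1 at 20%, 17.4 at 30% and 18.7 at 40%. These figures show how sensitive a six-patient rule is; they do not forecast this trial. This should be corrected, but it does not call the design into question.

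**What to change.** 1. In Section 6.1, reword the second limb so that an event is Not related when at least one of the three listed conditions holds.
2. Replace the laboratory presumption in Section 6.1 with investigator attribution of each laboratory adverse event, with no default to unrelated.
3. Record attribution on the five-level scale. For DLT counts and adverse event tables, collapse it to two: Definite, Probable and Possible are related; Unlikely and Unrelated are not. State this in Section 5.6 beside the DLT definition, and align the field in Section 6.5 with it.

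The DLT criteria themselves stay as they are; Sections 5.6, 6.1 and 6.5 must be reconciled on attribution only. The cost is protocol and eCRF wording. Sample size and error rates do not change. Reported rates of treatment-related laboratory toxicity may be somewhat higher.

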6.2 Serious Adverse Events

Serious Adverse Events will be reported per standard IRB reporting requirements.

Serious Unexpected problems will be reported per standard IRB reporting requirements.

Assessment of Intensity

Maximum intensity should be assigned to an adverse experience. Intensity will be assigned a grade of 1-5. Final arbitration of intensity in cases of differing assessments by different practitioners will be the attending physician. Day to day fluctuations of intensity may not be recorded but rather the worst grade over the longest time period may be recorded.

Assessment of Seriousness

Definition of Serious Adverse Experience (SAE)

A serious adverse drug experience is any adverse experience occurring at any dose that results in any of the following outcomes:

Death: Is immediately life threatening (immediate risk of death from the reaction as it occurred). This does not include a reaction that, had it occurred in a more severe form, might have caused death. Death due to disease progression or relapse is not considered an SAE unless the investigator deems it possibly related to study drug. Death due to progression of disease will be reported per MD Anderson IRB standard guidelines.

Disability/Incapacitation

Results in persistent or significant disability/incapacity (permanent or substantial disruption of a person's ability to conduct normal life functions).

Congenital anomaly/birth defect

Important medical events that may not result in death, be life-threatening, or require hospitalization may be considered a serious adverse drug experience when, based upon appropriate medical judgment, they may jeopardize the patient and may require medical or surgical intervention to prevent one of the outcomes listed in this definition. Examples of such medical events include allergic bronchospasm requiring intensive treatment in an emergency room or at home, blood dyscrasias or convulsions that do not result in inpatient hospitalization, or the development of drug dependency or abuse.

Hospitalization

In general, hospitalization signifies that the patient has been detained (usually involving at least an overnight stay) at the hospital or emergency ward for observation and/or treatment that would not have been appropriate in the physician's office or outpatient setting. When in doubt as to whether "hospitalization" occurred or was necessary, the adverse experience should be considered serious. Results in or prolongs an existing inpatient hospitalization. Hospitalization for elective surgery or routine clinical procedures** that are not the result of an adverse experience (e.g., elective surgery for a pre-existing condition) need not be considered adverse experiences and should be documented as appropriate. If anything untoward is reported during the procedure, that occurrence must be reported as an adverse experience, either 'serious' or 'non-serious' according to the usual criteria. New

hospitalization or prolonging of current hospitalization for disease progression or disease-related symptom management will not be considered a Serious Adverse Event.

****Routine Clinical Procedure:** one which is defined in the protocol as a procedure which may take place during the study period and should not interfere with the study drug administration or any of the ongoing protocol specific procedures.

SAE is any other important medical event that based upon appropriate medical judgement may jeopardize the patient or may require medical or surgical intervention to prevent one of the other outcomes listed in the definitions above. (e.g., may not result in death, be life-threatening, or require hospitalization).

The following are not considered hospitalizations for the purposes of assessing seriousness (however, one of the other serious criteria may apply):

- Hospitalizations for preplanned procedures;
- Hospitalization for study-related treatment and procedures.

Assessment of Causality

Every effort should be made by the investigator to explain clinically significant adverse experience and to assess its relationship, if any, to the study medication.

Immediate Reporting of Serious Adverse Experiences within 24 hours

Serious adverse experiences (SAEs) which occur at any time after first dose of study drug or performance of protocol mandated research procedure and within 30 days after receiving the last dose of study drug(s) or prior to commencement of new therapy will be reported to the IRB per institutional standard policy. All SAEs should be documented in the patient's medical records or on the institutional standard forms (immediate reporting versus AE log).

All patients with serious adverse experiences should be followed until resolution, stabilization, death, or commencement of new therapy.

Instances of death, cancer, or congenital abnormality brought to the attention of the Investigator at any time after cessation of study medication and considered by the Investigator to be possibly related to study medication should be reported to the MD Anderson Cancer Center Institutional Review Board within 30 days.

Serious Adverse Event (SAE) Reporting Requirements for M D Anderson Sponsor Single Site IND Protocol

An adverse event or suspected adverse reaction is considered "serious" if, in the view of either the investigator or the sponsor, it results in any of the following outcomes:

- Death
- A life-threatening adverse event
- Inpatient hospitalization or prolongation of existing hospitalization
- A persistent or significant incapacity or substantial disruption of the ability to conduct normal life functions.
- A congenital anomaly/birth defect.

Note: grade 3 and 4 eye related toxicities will be reported as SAEs.

Important medical events that may not result in death, be life-threatening, or require hospitalization may be considered a serious adverse drug experience when, based upon appropriate medical judgment, they may jeopardize the patient or subject and may require medical or surgical intervention to prevent one of the outcomes listed in this definition. Examples of such medical events include allergic bronchospasm requiring intensive treatment in an emergency room or at home, blood dyscrasias or convulsions that do not result in inpatient hospitalization, or the development of drug dependency or drug abuse (21 CFR 312.32).

- Important medical events as defined above, may also be considered serious adverse events. Any important medical event can and should be reported as an SAE if deemed appropriate by the Principal Investigator or the IND Sponsor, IND Office.
- All events occurring during the conduct of a protocol and meeting the definition of a SAE must be reported to the IRB in accordance with the timeframes and procedures outlined in “The University of Texas M. D. Anderson Cancer Center Institutional Review Board Policy on Reporting Adverse Events for Drugs and Devices”.
- Serious adverse events will be captured from the time of the first protocol-specific intervention, until 30 days after the last dose of drug, unless the participant withdraws consent.
- Serious adverse events must be followed until clinical recovery is complete and laboratory tests have returned to baseline, progression of the event has stabilized, or there has been acceptable resolution of the event.
- All SAEs, expected or unexpected/ initial or follow up, must be reported to the IND Office **within 5 working days of knowledge of the event** regardless of the attribution.
- Death or life-threatening events that are unexpected, possibly, probably or definitely related to drug must be reported (initial or follow up) to the IND Office **within 24 hours of knowledge of the event**
- Additionally, any serious adverse events that occur after the 30-day time period that are related to the study treatment must be reported to the IND Office. This may include the development of a secondary malignancy.
- The electronic SAE application (eSAE) will be utilized for safety reporting to the IND Office and MD Anderson IRB.
- All events reported to the supporting company must also be reported to the IND Office

Reporting to FDA:

- Serious adverse events will be forwarded to FDA by the IND Sponsor according to 21 CFR 312.32.

It is the responsibility of the PI and the research team to ensure serious adverse events are reported according to the Code of Federal Regulations, Good Clinical Practices, the protocol guidelines, the sponsor's guidelines, and Institutional Review Board policy.

Pregnancy

If a patient becomes pregnant while in the study, the study treatment must be immediately discontinued. Pregnancy information in a female patient (or for the female partner of a male patient) should be reported **as soon as possible** from the time the Investigator first becomes aware of a pregnancy or its outcome. This should be performed by completing a Pregnancy Form and faxing or e-mailing it to Taiho's Pharmacovigilance or designee. The eSAE application will be used to report pregnancy as "Other Important Medical Event" to the IND Office.

New and/or corrected information regarding the pregnancy obtained after submitting the Pregnancy Form must be submitted an updated Pregnancy Form to Taiho's Pharmacovigilance or designee. Pregnancies must be followed to outcome by the Investigator, even after study completion.

If the outcome of the pregnancy is a stillbirth, congenital anomaly/birth defect, or a serious event in the mother, it should be reported as an SAE to Taiho's Pharmacovigilance or designee. Live births will be followed up by the Investigator. Any information that may be associated with the study drug should be reported even after study completion.

Overdose

An overdose is defined as the accidental or intentional use of the drug in an amount higher than the dose being studied. An overdose or incorrect administration of study treatment is not itself an AE, but it may result in an AE. An overdose that results in an AE should be reported to Taiho's Pharmacovigilance or designee within 24 hours from the time the Investigator first becomes aware of its occurrence.

There is no known antidote available in case of futibatinib and pembrolizumab overdose. Overdose should be managed with close monitoring and administration of prophylactic and symptomatic therapies to prevent or correct potential side effects.

Investigator Communication with NCCN/Taiho Oncology, Inc.:

For expedited reports, Investigator- will send either the MedWatch report form or MD Anderson IND office eSAE report form to NCCN/Taiho Oncology, Inc. at the time of the regulatory authority submission to applicable regulatory authority (e.g.; US FDA) no later than seven (7) days for initial AND follow-up life-threatening and death reports, and fifteen (15) days for all other initial or follow-up serious and unexpected suspected adverse reactions (SUSARs), from the time of receipt of the SAE by Investigator-

All other SAEs/non-expedited Reports: For non-expedited SAE reports (i.e., unrelated to Study Drug or listed/expected event), Investigator- will send a quarterly safety line listing to NCCN/Taiho Oncology, Inc. within 10 days after the start of each quarter (e.g.; April 10th for Quarter 1 data due each year).

NCCN/Taiho Oncology, Inc. Email inbox for individual MedWatch report forms or MD Anderson IND office eSAE report forms and safety line listings: Investigator will send all individual SUSAR MedWatch reports or MD Anderson IND office eSAE report form and quarterly line listings to NCCN/Taiho Oncology, Inc. via email

